11. STATISTICAL CONSIDERATIONS

11.1. Study Design/Endpoints

This is a phase II study of high dose bolus interleukin-2 (HD IL2) in patients with advanced inoperable stage III or stage IV melanoma who have prior anti-PD1 immunotherapy. The safety of HD IL2 is well studied and will be monitored. The focus of the study is to evaluate the efficacy of this HD IL-2 in this specific patient population.

The primary endpoint is (CR+PR) as assessed by RECIST criteria version 1.1. The total accrual goal is 45 patients. We will follow a Bayesian design to establish sequential stopping rules for futility (Thall, Simon and Estey 1995). The expected response rate for this patient population is between 5 and 10%. We would consider the HD IL-2 worth further investigation if a response rate of 20% is achieved. Thus, if there is sufficient evidence that the response rate of the regiment is 7% or less, we will stop the accrual. Let p_0 and p_1 denote the response rate of the standard treatment and the HD IL-2 respectively, by sufficient evidence, we mean that the posterior probability, $\Pr(p_0 + 0.05 > p_1)$, exceeds 85%. Based on the existing data, it is safe to say that the response rate of the studied population under standard care is between 5 and 10%, therefore, we use a Beta(70,930) prior for the standard treatment, which corresponds to a distribution of the response rate centered at 7%. We set a flat prior, Beta(0.4,1.6), for the response rate of HD IL-2.

We will allow the accrual to continue without interruption for the first 10 patients. The stopping boundaries for futility after the “burning period” can be presented as tables of possible outcomes for efficacy as shown in the following table:

Table 1 Bayesian Stopping Rules

Stop the Accrual to if

Responses<=	in No. Pts
1	10-19
2	20-31
3	32-44
4	45

The operating characteristics of this design can expressed in terms of the probability of

stopping the study early when the regimen is effective (i.e. response rate>0.2) and ineffective (i.e. response rate<0.07) and the median sample size under each situation. The following table summarizes this probability and the median sample size under this design based on 10,000 simulations of hypothetical trials under different assumptions of true response rates.

Table 2 Frequentist Properties of the Stopping Rules

True Response Rate	Pr (Stop Early)	Median Sample Size
0.05	0.92	17.7
0.1	0.35	27.9
0.15	0.32	35.6
0.2	0.16	40.2
0.25	0.07	42.6
0.3	0.03	43.9

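### The text puts the futility threshold at a 7% response rate, but the formula that defines it tests against about 12%, and Table 1 follows neither

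*Combined protocol and SAP*

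**What the plan says.** All of this is in section 11.1 (Study Design/Endpoints) of the combined protocol and SAP.

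- Threshold in words: "if there is sufficient evidence that the response rate of the regiment is 7% or less, we will stop the accrual".
- Definition of the key term, in the next sentence: "by sufficient evidence, we mean that the posterior probability". The criterion is then given in full: "the posterior probability, $\Pr(p_0 + 0.05 > p_1)$, exceeds 85" per cent.
- Priors: "we use a Beta(70,930) prior for the standard treatment, which corresponds to a distribution of the response rate centered at 7" per cent, and "We set a flat prior, Beta(0.4,1.6), for the response rate of HD IL-2".
- Target: "We would consider the HD IL-2 worth further investigation if a response rate of 20% is achieved".
- Monitoring: "We will allow the accrual to continue without interruption for the first 10 patients", and "The total accrual goal is 45 patients".

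Table 1 then lists the stopping boundaries, and Table 2 gives stopping probabilities and sample sizes from 10,000 simulated trials. Introducing Table 2, the section describes an ineffective regimen as one with a rate below 0.07. Section 11.2 also uses 7%, as the standard-care rate in the final test. The figure of 12% appears nowhere, and the 0.05 margin is not explained.

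**The concern.** A phrase that defines sufficient evidence should fix how sure one must be. This one also moves the threshold, from 7% to 5 points above the standard rate. A monitoring committee that relies on the sentence would believe accrual stops only when the regimen looks no better than standard care. Under the formula, accrual can stop when that belief is not supported. At 3 responses in 42 patients the posterior probability that p1 is below p0 + 0.05 is 0.855, which triggers a stop, while the probability that p1 is below p0 is only 0.49.

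Staff would normally look to the printed boundary table to settle such a conflict. Here they cannot, because Table 1 agrees with neither version.

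**Working it through.** **Inputs (section 11.1).** p0 ~ Beta(70, 930), mean 70/1000 = 0.07, 95% interval 0.055 to 0.087. p1 prior Beta(0.4, 1.6), mean 0.20. Margin 0.05, cutoff 0.85, monitoring from patient 10, maximum 45. I assume a check after every patient with responses known at once.

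**Formula.** After r responses in n patients, p1 ~ Beta(0.4 + r, 1.6 + n − r). The stopping quantity is Pr(p0 + d > p1) = ∫ f(u) F(u + d) du, where f is the Beta(70, 930) density and F is the posterior distribution function of p1. Use d = 0.05 for the stated formula and d = 0 for the same rule without its margin. Operating characteristics come from exact binomial recursion.

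**Boundaries (stop if responses are at or below).**
- d = 0.05: 0 in 10–18, 1 in 19–30, 2 in 31–41, 3 in 42–45. A fixed cut at 0.07 + 0.05 = 0.12 gives the same boundary.
- d = 0: no stop at 10, then 0 in 11–34 and 1 in 35–45. A fixed cut at 7% is almost the same (0 in 11–33, 1 in 34–45).
- Table 1 as printed: 1 in 10–19, 2 in 20–31, 3 in 32–44, 4 at 45.

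**Reproducing Table 2** (probability of stopping / sample size; computed sizes are means):

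| True rate | Table 2 | d = 0.05 | d = 0 |
|---|---|---|---|
| 0.05 | 0.92 / 17.7 | 0.92 / 17.7 | 0.67 / 24.7 |
| 0.10 | 0.35 / 27.9 | 0.60 / 27.9 | 0.34 / 34.0 |
| 0.15 | 0.32 / 35.6 | 0.32 / 35.6 | 0.17 / 39.2 |
| 0.20 | 0.16 / 40.2 | 0.155 / 40.2 | 0.087 / 42.1 |
| 0.25 | 0.07 / 42.6 | 0.07 / 42.6 | 0.04 / 43.6 |
| 0.30 | 0.03 / 43.9 | 0.03 / 43.9 | 0.02 / 44.3 |

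The formula matches every sample size and five of six probabilities. The column is labelled as a median but holds means; the formula's medians are 10, 31, 45, 45, 45 and 45. In the 0.10 row the printed 0.35 lies near the d = 0 value, but the 27.9 beside it fits only d = 0.05.

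**Rates not in Table 2** (probability of stopping, d = 0.05 against d = 0): 0.81 against 0.52 at 7%; 0.74 against 0.45 at 8%; 0.48 against 0.26 at 12%.

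**Power at a true 20%.** The section 11.2 test (exact, one-sided, alpha 0.1, 45 patients) rejects at 6 or more responses. With no stopping, alpha is 0.092 and power 0.91. Power is 0.81 with d = 0.05 and 0.85 with d = 0.

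**Table 1 against the formula.** Formula posteriors at its printed stopping points are 0.60 at 1/10, 0.63 at 2/20, 0.69 at 3/32 and 0.76 at 4/45, all below 0.85. Run as printed, it stops with probability about 0.42 at a true 20%, with mean size 30.9 and power 0.57.

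**The case against.** The strongest reply is that the plan has only one operational rule. The 7% sentence gives no probability cutoff, and its key term is defined at once by the formula, so the formula governs. That largely stands. The d = 0 rule is my construction: it borrows the formula's priors and its 0.85 cutoff. The comparison shows how far the wording is from the formula; it does not show two rules that the plan specifies.

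A margin over the standard rate is also a normal feature of such designs, and it is coherent with a 20% target. A reader might infer that the formula is invalid. Nothing in the documents supports that.

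A reader might also infer that the plan treats every rate from 8% to 12% as futile. It does not. Stopping is a matter of probability, and at a true 12% the trial more often continues than stops (0.48). The zero-margin version also stops at these rates, less often. Rates of 8% to 10% lie within the plan's own 5–10% range for standard care, and all of 8–12% falls well short of 20%.

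At the 20% target the difference is modest: 0.155 against 0.087 for early stopping, and about 4 points of power.

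Finally, a committee would probably work from Table 1, where the departure is larger. That is true, and the size of the Table 1 discrepancy should not be charged to this sentence. Reading its heading as fewer than, instead of at most, gives about 0.145 and 40.4 at a true 20%. That is close to Table 2 but not equal to it, so a misprinted heading is possible but unconfirmed.

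What remains is a decision threshold stated as 7% and defined at about 12%, which no other section reconciles.

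**Conclusion.** The concern holds as a misdescription of the futility threshold. The words say 7%; the defining formula tests against about 12%. Table 2 indicates that the formula is the rule that was simulated, with one exception to be declared: the 0.10 row's 0.35, where the formula gives 0.60.

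Taking the margin out lowers early stopping by 29 points at a true 7% (0.81 − 0.52), 26 points at 10% (0.60 − 0.34) and about 7 points at 20% (0.155 − 0.087). So the wording matters most at low rates, where stopping is largely wanted, and less at the target.

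The conclusion that the two thresholds differ needs no modelling. The sizes rest on the stated priors, the 0.85 cutoff, and checks after each patient from 10 to 45. The sponsor's intent is inferred from Table 2. Because Table 1 fits neither version, it cannot be used to decide which was meant.

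**What to change.** 1. Reword the sentence: accrual stops when the posterior probability that p1 is below p0 + 0.05 (about 12%) exceeds 85%. Add a line justifying the 5-point margin against the 20% target.
2. Replace Table 1 with the boundaries computed from that formula: 0 responses in 10–18 patients, at most 1 in 19–30, at most 2 in 31–41, at most 3 in 42–45.
3. Correct the stopping probability in the 0.10 row of Table 2 to about 0.60.
4. If 7% was intended, remove the 0.05 and regenerate both tables.

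The cost is wording and recomputation, with no extra patients. The downside is candour: the plan would state openly that it will often stop for regimens modestly better than 7%, about 74% of the time at a true 8% and 48% at 12%.

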- f: Off study evaluation. Patients will be followed for 5 years after removal from study or until death, whichever occurs first. The frequency and the type of evaluations during this follow up period will follow institutional standard of care practices. For patients who wish not to follow with a study investigator, they can be followed by their treating physician of choice and also following local standard of care practices. Data on disease progression and survival will be collected on all patients every 3-6 months.

For the purposes of this study, patients should be reevaluated for response at the end of each course 1 (8 weeks +/- 1 week). Following completion of treatment, and in the absence of disease progression will be done every 12 weeks +/- 2week during the observation phase for the first 2 years, then every 6 months (-/+ 2 weeks) for years 3-5, then yearly (-/+ 4 weeks) afterwards.

MRI or contrast CT of the brain is not required but should be done as clinically indicated. For those subjects who have progressed, Data on survival will be collected on all patients every 6months for 5 years.

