11.2. Sample Size/Accrual Rate

We plan 12-15 months of accrual for 45 patients (approximately 3-4 patients per month) and a minimum of 6 months follow-up.

Evaluable patients include study subjects who received at least one cycle of HD IL-2 and had later formal imaging and clinical assessment of tumor response to treatment and those who failed to return for imaging because of cancer specific death or clinical determination of progression. Non-evaluable subjects will be replaced.

With 45 evaluable subjects, we will have >90% power to declare a significant difference between an response rate of 20% or higher and 7% (the expected response rate of this population under standard care) by a 1-sided exact binomial test ($\alpha=0.1$).

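### Table 2 assumes every response is known at once, but the first scan is at week 8 with 3-4 patients entering per month; the futility rule does not say who counts or whether accrual waits

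*Combined protocol and SAP*

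**What the plan says.** Section 11.1 sets the target with "The total accrual goal is 45 patients". It stops accrual for futility when the posterior probability that HD IL-2 is less than 5 points better than standard care exceeds 85%. The priors are given as "we use a Beta(70,930) prior for the standard treatment" and "We set a flat prior, Beta(0.4,1.6), for the response rate of HD IL-2". The rule starts after a run-in: "We will allow the accrual to continue without interruption for the first 10 patients". Table 1 then lists a maximum number of responses against a number of patients, for every count from 10 to 45. Table 2 is introduced with "The following table summarizes this probability and the median sample size under this design based on 10,000 simulations". The simulations are described by true response rate only; no accrual rate or assessment delay is mentioned.

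The timing is given elsewhere. Section 9 says "patients should be reevaluated for response at the end of each course 1 (8 weeks +/- 1 week"). Section 11.2 says "We plan 12-15 months of accrual for 45 patients (approximately 3-4 patients per month").

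Section 11.1 does not say whether the Table 1 count is of enrolled or assessed patients, how patients awaiting a scan are treated, or whether accrual pauses for them.

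**The concern.** A rule that looks after every patient works as simulated only if each result is in hand before the next patient enters. Here the first result comes about 1.8 months after treatment starts. Either accrual runs on while scans are pending, and more patients enter than Table 2 states before the rule can act, or accrual is held and the timetable fails. At stake are the number of patients given an intensive inpatient regimen if it proves inactive, and whether two teams holding the same data would reach the same decision on accrual.

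**Working it through.** **Inputs.** From Section 11.1: maximum 45 patients, looks from patient 10, threshold 0.85, margin 0.05, priors Beta(70,930) and Beta(0.4,1.6). From Section 11.2: 3-4 patients per month. From Section 9: first assessment at 8 weeks, which is 8/4.345 = 1.84 months.

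**1. Boundaries from the stated criterion.** With r responses in n patients, p1 has posterior Beta(0.4 + r, 1.6 + n − r). The trial yields no data on p0, so p0 keeps its prior. Stop if

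Pr(p0 + 0.05 > p1) = ∫ f(x) F(x + 0.05) dx > 0.85,

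where f is the Beta(70,930) density and F the posterior distribution function of p1. Values near the boundary are: 0/10, 0.93; 1/18, 0.833; 1/19, 0.851; 2/30, 0.842; 2/31, 0.856; 3/41, 0.844; 3/42, 0.855. The rule is therefore: stop at 0 responses in 10-18 patients, at most 1 in 19-30, at most 2 in 31-41, at most 3 in 42-45.

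**2. Reproducing Table 2 with no delay.** An exact binomial recursion was used, with a look after each patient from 10 to 44.

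**3. Adding the delay.** Trials were simulated with Poisson accrual at 3 to 4 per month, a fixed 8-week lag, the step 1 boundaries, only assessed patients counted, and accrual continuing. Early here means before 45 are enrolled. Cells show probability of early stopping / sample size.

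| True rate | Table 2 | No lag (mean) | 8-week lag (mean) |
|---|---|---|---|
| 0.05 | 0.92 / 17.7 | 0.916 / 17.7 | about 0.87 / 22.6-24.4 |
| 0.10 | 0.35 / 27.9 | 0.603 / 27.9 | 0.56-0.58 / 31.1-32.1 |
| 0.15 | 0.32 / 35.6 | 0.320 / 35.6 | 0.29-0.31 / 37.2-38.1 |
| 0.20 | 0.16 / 40.2 | 0.155 / 40.2 | 0.15-0.16 / 41.0-41.4 |
| 0.25 | 0.07 / 42.6 | 0.073 / 42.6 | 0.07 / 43.0-43.2 |
| 0.30 | 0.03 / 43.9 | 0.034 / 43.9 | 0.03-0.04 / 44.0-44.2 |

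The no-lag column matches all six sample sizes and five of six probabilities. The exception is 0.35 at a true 10%, which computes as 0.60. The column labelled median holds means; the no-lag medians are 10, 31, 45, 45, 45 and 45.

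**4. Patients pending.** 3 × 1.84 = 5.5 and 4 × 1.84 = 7.4. When the tenth patient is scanned, about 15.5-17.4 are enrolled.

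**5. Extra enrolment.** At a true 5%: 22.6 − 17.7 = 4.9 to 24.4 − 17.7 = 6.7. At 10%: 31.1 − 27.9 = 3.2 to 32.1 − 27.9 = 4.2.

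**6. Holding accrual instead.** Waiting for the scan after each of patients 10 to 44 adds 35 × 1.84 = 64.4 months. Accrual would take 45/4 + 64.4 = 75.6 to 45/3 + 64.4 = 79.4 months, against the planned 12-15. Holds every 5 patients give about 24-28 months, and every 10 about 19-22.

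**7. Late responses.** Section 11.3.3 uses best response over up to three courses. Suppose 10%-30% of responses are first seen after course 2 and credited at week 16 (both are assumptions). Early stopping at a true 20% is then about 0.17-0.26.

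**8. Separate from the delay.** Printed Table 1 allows one more response than step 1 at most sample sizes. It stops at 1/10 and 2/20, where the posterior is only 0.60 and 0.63. With no lag it stops 0.415 of trials at a true 20%. With the lag and assessed counting the figure is still 0.41-0.42.

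**The case against.** The strongest reply is that the documents already point to assessed patients. Section 10.1.1 requires re-evaluation of disease, or earlier objective progression. Section 11.2 defines evaluable patients by later imaging and clinical assessment, or by cancer death or clinical progression, and replaces the others. Section 11.3.1 leaves out of the response rate patients not imaged for other reasons. On that reading the delay costs almost nothing when the regimen works. This stands, and it limits the point. None of those passages expressly governs the Table 1 count, so a clarification is still needed.

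The run-in sentence may also hint at later pauses, under which Table 2 would hold. No pause is defined, and waiting for every result does not fit the accrual plan.

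A reader might infer that the rule would close most trials of a regimen with a true 20% response rate. If pending patients were counted as non-responders, early stopping would indeed be about 0.58-0.76 with the step 1 boundaries. That is a worst case: the text does not exclude it, but the evaluability definitions make it the less natural reading. Still higher figures arise from applying printed Table 1 in the same way, but they mix in the separate boundary mismatch.

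A reader might also treat late responses as never counted. That amounts to true rates of 0.20 × 0.90 = 0.18 and 0.20 × 0.70 = 0.14, with no-lag stopping of 0.21 and 0.37. Section 5.1 assesses response after every course, so late responses enter later looks.

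**Conclusion.** The concern holds in a limited form. Table 2 omits a delay that the plan itself contains, and its sample sizes at low response rates are too favourable by about 3-7 patients. Early stopping at a true 5% is about 5 points lower than stated. At a true 20% nothing material changes.

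These sizes assume Poisson accrual at the planned rate, a fixed 8-week lag, assessed patients only, continuing accrual, and boundaries from the 0.85 criterion. The lag excludes the up to 2 weeks from registration to first dose that Section 4.1 allows.

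The delay is not the only reason Table 2 is not delivered: printed Table 1 departs from the stated criterion even with no lag. The documents do not support the claim that the rule as planned would usually close a trial of an active regimen. This should be fixed, because the denominator of a rule that closes accrual must be explicit and its stated properties should match the trial's own timetable.

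**What to change.** In Section 11.1:

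- State that the Table 1 count includes only patients with a response assessment, or with progression or cancer death before it, and that enrolled but unassessed patients are not counted as non-responders.
- State whether accrual continues while scans are pending. If it is to be held, say when, and revise the 12-15 month plan to match.
- Reconcile Table 1 with the 0.85 criterion. Then re-run Table 2 with the 8-week lag and 3-4 patients per month, restate both columns (including the 0.35 at a true 10%), and label the sample size as a mean.

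The cost of the delay point is one or two sentences and one re-simulation. The stated expected sample sizes become about 3-7 patients less favourable at low response rates. If accrual continues while scans are pending, the maximum sample size, endpoint and accrual plan need not change.

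### Table 1's futility limits are one response too high for the stated posterior rule at 31 of 36 looks; at a true 20% response rate they stop about 42% of trials early, not the stated 16%

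*Combined protocol and SAP*

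**What the plan says.** All of the relevant text is in Section 11.1 of the combined protocol and SAP.

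- **Rule.** "by sufficient evidence, we mean that the posterior probability, $\Pr(p_0 + 0.05 > p_1)$, exceeds 85" per cent. Here p0 is the response rate on standard treatment and p1 the rate on HD IL-2.
- **Priors.** "we use a Beta(70,930) prior for the standard treatment, which corresponds to a distribution of the response rate centered at 7" per cent, and "We set a flat prior, Beta(0.4,1.6), for the response rate of HD IL-2".
- **Looks.** "We will allow the accrual to continue without interruption for the first 10 patients", and "The total accrual goal is 45 patients". The ranges in Table 1 imply a look after every patient from the 10th.
- **Limits.** "Table 1 Bayesian Stopping Rules" lists the number of responses at or below which accrual stops: 1 in 10–19 patients, 2 in 20–31, 3 in 32–44, 4 in 45.
- **Operating characteristics.** "Table 2 Frequentist Properties of the Stopping Rules" gives the probability of early stopping as 0.92, 0.35, 0.32, 0.16, 0.07 and 0.03 at true rates of 0.05, 0.10, 0.15, 0.20, 0.25 and 0.30. The sample sizes are 17.7, 27.9, 35.6, 40.2, 42.6 and 43.9.
- **Verbal description.** "if there is sufficient evidence that the response rate of the regiment is 7% or less, we will stop the accrual".

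**The concern.** The rule, the priors and the first look fix the stopping limits completely, so Table 1 should follow from them and Table 2 should follow from Table 1. The first printed limit already looks too aggressive: it closes accrual at 1 response in 10, an observed rate of 10%, when the prior for HD IL-2 carries the weight of only two patients and the comparison threshold is about 12%.

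Table 1 is the part of the design that staff can apply without software. If it does not represent the rule, the trial has a different risk of abandoning an active regimen from the one stated, and the power claim in Section 11.2 is affected as well.

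**Working it through.** **Inputs (all from Section 11.1).** p0 ~ Beta(70, 930), mean 0.07. p1 ~ Beta(0.4, 1.6), mean 0.20. Margin 0.05, cut-off 0.85, first look at n = 10, maximum n = 45.

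**Step 1: limits implied by the rule.** After x responses in n patients, p1 ~ Beta(0.4 + x, 1.6 + n − x). The posterior probability is

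Pr(p0 + 0.05 > p1 | x, n) = ∫ f(t; 70, 930) · F(t + 0.05; 0.4 + x, 1.6 + n − x) dt,

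where f and F are the Beta density and distribution function. The limit at each n is the largest x for which this exceeds 0.85.

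| Stop if responses ≤ | Rule: n | Table 1: n |
|---|---|---|
| 0 | 10–18 | none |
| 1 | 19–30 | 10–19 |
| 2 | 31–41 | 20–31 |
| 3 | 42–45 | 32–44 |
| 4 | none | 45 |

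The two agree only at n = 19, 31, 42, 43 and 44. At the other 31 looks the printed limit is one response higher.

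**Step 2: posterior probability at the printed limits.** At the start of each band: 1/10 gives 0.605, 2/20 gives 0.630, 3/32 gives 0.695, 4/45 gives 0.756. Just before the two tables come into line: 1/18 gives 0.833, 2/30 gives 0.842, 3/41 gives 0.844. The shortfall from 0.85 is large early in each band and small late in it. At all of these points the stated rule does not stop.

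**Step 3: operating characteristics.** These come from exact forward recursion on the binomial path, with a look after each patient from n = 10 to n = 44. Trials still running then count as N = 45.

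| True rate | Table 2: stop / N | Rule: stop / mean N | Table 1 as printed: stop / mean N |
|---|---|---|---|
| 0.05 | 0.92 / 17.7 | 0.916 / 17.7 | 0.975 / 11.7 |
| 0.10 | 0.35 / 27.9 | 0.603 / 27.9 | 0.830 / 17.2 |
| 0.15 | 0.32 / 35.6 | 0.320 / 35.6 | 0.616 / 24.4 |
| 0.20 | 0.16 / 40.2 | 0.155 / 40.2 | 0.415 / 30.9 |
| 0.25 | 0.07 / 42.6 | 0.073 / 42.6 | 0.262 / 36.0 |
| 0.30 | 0.03 / 43.9 | 0.034 / 43.9 | 0.156 / 39.6 |

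The rule reproduces Table 2 in eleven of twelve entries. The exception, 0.35 at a true rate of 0.10, fits neither set of limits and looks like a misprint. Table 2 heads its last column as a median, but the values are means: the rule's medians at 0.05, 0.10, 0.15 and 0.20 are 10, 31, 45 and 45.

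**Step 4: where the difference arises.** Most of it is at the first look. At a true rate of 20%, Pr(≤ 1 of 10) = 0.8¹⁰ + 10 × 0.2 × 0.8⁹ = 0.107 + 0.268 = 0.376. The rule stops only at 0 of 10, with probability 0.107.

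**Step 5: effect on power.** Section 11.2 claims more than 90% power at 45 evaluable patients for 20% against 7% with one-sided α = 0.1. Requiring at least 6 responses gives α = 0.092 and power 0.910 when stopping is ignored. The probability of reaching 45 patients with at least 6 responses at a true 20% is 0.573 under Table 1 as printed and 0.807 under the stated rule.

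**The case against.** The strongest counter-argument is that only the comparison sign is wrong. With strictly-less-than in the column head, Table 1 becomes 0 in 10–19, ≤ 1 in 20–31, ≤ 2 in 32–44 and ≤ 3 at 45. That agrees with the rule at 31 of 36 looks and stops 14.3% of trials at a true 20%, with mean N 40.4. This is a plausible origin of the error, but it does not rescue the table: the printed sign is still wrong, and changing it alone does not recover Table 2. At a true 5% it gives 0.865 and 18.3, against the stated 0.92 and 17.7, because the band ends also differ from the rule's.

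A different parameter choice might be thought to explain Table 1. Alternative margins, cut-offs, priors for p1 and look schedules were tried, and none reproduced it. With looks every 5, 10 or 15 patients, the printed limits still stop 41%, 41% and 39% of trials at a true 20%.

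Three smaller points stand as qualifications:

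- The stopping probabilities are nominal. They assume each response is known before the next patient is counted, whereas response is first assessed at week 8 and planned accrual is 3–4 patients a month. Table 2's figures are reproduced under the same assumption, so the comparison is like for like.
- The entry at n = 45 cannot stop accrual early, because accrual is then complete.
- The verbal reference to a rate of 7% or less is loose wording that the formula then overrides, so it is secondary to the table error.

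**Conclusion.** Table 1 is wrong as written. It does not follow from the posterior rule in the same section, and Table 2 shows that the rule, not Table 1, is the design that was evaluated. Followed as printed, it raises the probability of stopping a regimen with a true 20% response rate from 15.5% (16% stated) to 41.5%, about 2.7 times (0.415/0.155). At 25% the increase is from 7.3% to 26.2%, and at 30% from 3.4% to 15.6%.

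The result rests on the priors, margin and cut-off as stated, a look after every patient from the 10th, and immediate knowledge of response. Delayed response assessment could change the realised stopping rates, but it would not make the table consistent with the rule. This must be corrected before the table is used for any accrual decision.

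**What to change.** Replace Table 1 with the limits the stated rule generates: stop at 0 responses in 10–18 patients, 1 or fewer in 19–30, 2 or fewer in 31–41, and 3 or fewer in 42–45. State whether the counts refer to evaluable patients; Section 11.2 replaces non-evaluable subjects, but Table 1 counts only patients.

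In the same amendment:

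- Reword the verbal description to match the formula: accrual stops when there is more than 85% posterior probability that the HD IL-2 response rate is less than 5 percentage points above standard, that is, below about 12% (0.07 + 0.05). Applied literally, a 7% threshold would stop only at 0 in 11–34 and 1 or fewer in 35–45.
- Correct the Table 2 stopping probability at a true rate of 0.10 (0.60 by this calculation, 0.35 printed) and relabel the sample-size column as a mean.

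The cost is a protocol correction and a re-run of the design software to confirm the limits. The maximum stays at 45. Relative to the printed table, the expected sample size for an inactive regimen rises (at a true 5%, from 11.7 to 17.7), which is the figure Table 2 already reports.

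### Table 2 contradicts itself at a 10% response rate (0.35 stopping early cannot go with a sample size of 27.9), and its 'median' column holds means

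*Combined protocol and SAP*

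**What the plan says.** Section 11.1 sets a Bayesian futility rule for the response rate. Accrual stops when "the posterior probability, $\Pr(p_0 + 0.05 > p_1)$, exceeds 85" percent. The priors are given as "we use a Beta(70,930) prior for the standard treatment" and "We set a flat prior, Beta(0.4,1.6), for the response rate of HD IL-2". The first look comes at 10 patients ("We will allow the accrual to continue without interruption for the first 10 patients") and the ceiling is 45 ("The total accrual goal is 45 patients"). Table 1 then lists stopping boundaries by number of patients.

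Table 2 is introduced with "The following table summarizes this probability and the median sample size under this design based on 10,000 simulations of hypothetical trials". Its entries (true rate: probability of stopping early / median sample size) are:

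- 0.05: 0.92 / 17.7
- 0.10: 0.35 / 27.9
- 0.15: 0.32 / 35.6
- 0.20: 0.16 / 40.2
- 0.25: 0.07 / 42.6
- 0.30: 0.03 / 43.9

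The text before the table and the column header both call the last column a median. Nothing elsewhere in the document corrects or explains these figures.

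**The concern.** The probability of stopping falls from 0.92 to 0.35 between rates of 5% and 10%, then barely moves, to 0.32, at 15%. Over the same step from 10% to 15% the sample size rises by almost 8 patients. Those two movements do not fit together. The sample sizes also carry decimals that a median of whole patient counts cannot have.

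Table 2 is the plan's only description of how the futility rule performs. The suspect cell sits at the top of the range given for standard care: "The expected response rate for this patient population is between 5 and 10" percent. A reader there would conclude that about one trial in three stops early. A reader of the last column would also misjudge the typical size of the trial.

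**Working it through.** **Checks that need no model.** No trial stops before 10 patients and none exceeds 45. Hence

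mean N ≥ 10 × Pr(stop) + 45 × (1 − Pr(stop)) = 45 − 35 × Pr(stop).

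- With Pr(stop) = 0.35: mean N ≥ 45 − 12.25 = 32.75. If 0.35 was rounded down from 0.355, the bound is 32.6. The table prints 27.9.
- Turned round, a mean of 27.9 needs Pr(stop) ≥ (45 − 27.9)/35 = 0.489.
- If 27.9 is a median, at least half the trials must stop early. With Pr(stop) = 0.35, 65% of trials run to 45, so the median is 45.
- The median of 10,000 whole numbers is a whole or half number. None of 17.7, 27.9, 35.6, 40.2, 42.6 and 43.9 is.
- In the rows from 0.15 to 0.30 the printed Pr(stop) is at most 0.32, so each median must be 45.

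**Reproducing the table from the stated criterion.** The inputs are all from Section 11.1: p0 ~ Beta(70,930); p1 ~ Beta(0.4 + r, 1.6 + n − r) after r responses in n patients; stop if Pr(p0 + 0.05 > p1) > 0.85. I assumed a look after every patient from the 10th, which fits a sequential rule and the unbroken patient ranges in Table 1.

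Numerical integration over p0 gives the posterior probabilities at the turning points: 1/10 = 0.605, 1/18 = 0.833, 1/19 = 0.851, 2/30 = 0.842, 2/31 = 0.856, 3/41 = 0.844, 3/42 = 0.855, 4/45 = 0.756. The boundary is therefore 0 responses at 10–18 patients, ≤1 at 19–30, ≤2 at 31–41 and ≤3 at 42–45.

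Exact recursion over the number of responses, counting stops before patient 45, gives:

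| True rate | Pr(stop), printed | Pr(stop), exact | Sample size, printed | Mean, exact | Median, exact |
|---|---|---|---|---|---|
| 0.05 | 0.92 | 0.916 | 17.7 | 17.69 | 10 |
| 0.10 | **0.35** | **0.603** | 27.9 | 27.88 | 31 |
| 0.15 | 0.32 | 0.320 | 35.6 | 35.59 | 45 |
| 0.20 | 0.16 | 0.155 | 40.2 | 40.18 | 45 |
| 0.25 | 0.07 | 0.073 | 42.6 | 42.63 | 45 |
| 0.30 | 0.03 | 0.034 | 43.9 | 43.88 | 45 |

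All six sample sizes match as means, and five of the six probabilities match. The exception misses by 0.25. The Monte Carlo standard error with 10,000 trials is √(0.6 × 0.4/10,000) ≈ 0.005, so chance does not explain it.

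The chance of 0 responses in the first 10 patients at a 10% rate is 0.9^10 = 0.349. The printed 0.35 may be that first-look probability or a typing error; the document does not say.

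**Alternatives.** None gives 0.35 together with 27.9.

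- Table 1 as printed gives Pr(stop) of 0.97, 0.83, 0.62, 0.42, 0.26, 0.16 and means of 11.7, 17.2, 24.4, 30.9, 36.0, 39.6, which match no row.
- Table 1 read as strictly fewer responses gives 0.545 at 10%, or 0.578 counting a stop at 45.
- Dropping the 0.05 margin gives 0.344 at 10%, but with a mean of 34.0, and the neighbouring rows become 0.665 (printed 0.92) and 0.174 (printed 0.32).

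**The case against.** The fair defence is that this is one wrong cell and one wrong header. Under the criterion, the rows at 5% and 20%, which come nearest to the plan's own ineffective (below 7%) and effective (above 20%) cases, are correct once the column is read as means. The design compares 7% with 20%, so no boundary or power statement uses the 10% cell; the power claim in Section 11.2 rests on a separate exact binomial test. Against the criterion, 0.35 understates how often a weak regimen is stopped, so it hides no added patient risk. Reporting a mean is legitimate. All of this stands, and it limits the weight of the point.

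Two cautions about the correction also stand. The value 0.60 belongs to the posterior criterion; if Table 1 governs as printed, 0.60 is not the right replacement. The conflict between Table 1 and the criterion is a separate defect and should not add weight to this one. And the median of 31 at 10% is fragile: exact cumulative stopping is 0.4988 from patient 19 and next rises, to 0.5624, at patient 31, so a fresh run of 10,000 trials would return 19 about 41% of the time. Relabelling the column as means is the safer repair.

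None of this rescues the printed row, which is impossible under any boundary. Text extraction is an unlikely cause: the table is complete and the running text also says median.

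**Conclusion.** The concern holds. Two conclusions need only the first look at 10 patients, the ceiling of 45 and whole-number sample sizes: 0.35 and 27.9 cannot belong to the same row, and the last column does not hold medians.

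The replacement value depends on which boundary governs. Under the posterior criterion, with a look after every patient, the probability at 10% is 0.60, about 25 percentage points above the printed figure. The 11 matching entries strongly support that reading as the source of the table. Under the same criterion the typical trial stops at 10 patients when the rate is 5% (17.7 printed) and runs to 45 when it is 20% (40.2 printed). If Table 1 governs instead, every row of Table 2 is wrong.

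The error is definite and worth correcting, because these are the only operating characteristics given. Taken alone it does not change conduct.

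**What to change.** 1. Reconcile the posterior criterion with Table 1. At 1 response in 10 patients Table 1 stops accrual, while the posterior probability is 0.605, below the 0.85 threshold.
2. Regenerate Table 2 from the boundary that governs.
   - *Posterior criterion:* change 0.35 to 0.60 and relabel the last column as mean sample size, in the header and in the text. If medians are preferred, print 10, 31, 45, 45, 45, 45 from exact calculation, since simulation may give 19 for the second.
   - *Table 1 as printed:* replace all six rows with the probabilities and means shown above for that boundary; its medians are 10, 10, 10, 45, 45, 45.
3. State the look schedule and whether a stop at patient 45 counts as early.
4. Optionally, add a row at the 7% null rate (posterior criterion: 0.80, mean 21.9, median 19). Its absence is not an error.

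Correcting Table 2 costs a text change. Step 1 may alter conduct if Table 1 is amended.
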